11.4. Pre-planned sensitivity analyses

If the percentage of patients excluded from PP is superior to 10% in at least one treatment arm, all efficacy analyses will be repeated in the PP population.

At both final and long term follow-up analyses and for both PFS and OS, the stratified LogRank test and the Cox's proportional hazards model will also be computed stratified by the stratification factors assessed at randomization (except institution) and MGMT methylation status in the ITT population.

Other exploratory analyses may be performed on the basis of subgroups of patients (see section 11.5), but results of these exploratory analyses may not serve as a basis for drawing conclusions concerning protocol efficacy.

11.5. Subgroup Analyses

Overall survival and PFS will also be analyzed within the following subgroups:

- MGMT
- Age (≤ 55 , >55 years),

- Sex (male, female),
- Karnofsky performance status (70/80, 90/100),
- MMSE (≤ 27 , > 27),
- Baseline steroid use (yes, no),
- Extent of surgery (partial/biopsy, gross total).

Additional subgroup analyses based on other baseline disease characteristics might be performed as appropriate.

12. Safety Analysis

All safety analyses will be conducted using the SP.

The safety and tolerability will be followed from study treatment initiation through up to 30 days after the last administration of study treatment. The safety analyses will be reported for the whole study time and by treatment period for the safety analysis as defined below:

The concomitant period (TMZ/RT or TMZ/RT+MRZ) will start on the day of the first administration of radiation therapy and end 27 days after the day of the last administration of radiation therapy and before the start of adjuvant TMZ period whichever occurred first.

The adjuvant TMZ period (ie, when TMZ is administered alone or with MRZ) will start on the day of the first dose of adjuvant TMZ and end up to 27 days after the first day of administration of the last cycle of adjuvant TMZ

The maintenance MRZ period (ie, when MRZ is administered alone after discontinuation of TMZ) will start 28 days after the first day of administration of the last cycle of adjuvant TMZ and end up to 27 days after the first day of administration of the last cycle of maintenance MRZ.

The follow-up period (ie, when all treatments are discontinued) will start 28 days after the first day of administration of the last cycle of maintenance MRZ or adjuvant TMZ up to 30 days after the last treatment administration (MRZ or TMZ)

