## 5.3 Treatment duration

In the standard arm, patients will receive up to 6 cycles of TMZ as maintenance at a dose of 150-200 mg/m^2 daily for 5 days every 28 days, unless treatment is discontinued for disease progression, unacceptable toxicity, or withdrawal of consent.

Continuation of maintenance temozolomide beyond 6 cycles (e.g., for a maximum of 12 cycles) is not encouraged but is left to the discretion of the Investigator and the interest of the patient.

In the experimental arm, patients will receive up to 6 cycles of MRZ+TMZ in the maintenance setting, followed by another 12 cycles of MRZ alone, unless treatment is discontinued for disease progression, unacceptable toxicity, withdrawal of consent, or the patient has completed the 18 cycles of MRZ as planned. In the event that one drug (TMZ or MRZ) is discontinued for reasons other than disease progression, the other will then continue as a single agent.

At study closure, all study participants may continue to receive study treatment as planned in the protocol (see chapter 4) provided that they benefit from it and all protocol-specified criteria for continuing study treatment are met. For all patients who discontinue treatment for reasons other than disease progression, whenever possible, tumor assessment will continue as per protocol until disease progression, or start of a new treatment regimen.

After disease progression, treatment will be left to the discretion of the treating physician. Any further anti-cancer therapy will not be considered as part of the protocol treatment. However, patients will be followed for survival and the start of first new anti-GBM therapy and its outcome.

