## 5.5 Dose and schedule modifications

Treatment (MRZ +TMZ) may be administered -1 / +3 days of a scheduled dose for reasons other than toxicity.

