5.1. Overall Study Design and Plan

This is a multicenter, randomized, controlled, open-label Phase 3 superiority trial with a safety monitoring plan and an early stopping rule for futility.

After signing the informed consent form and upon confirmation of the subject eligibility, subjects were randomized 1:1 to the experimental arm, referred to as (MRZ/TMZ/RT)→MRZ/TMZ, or to the control arm (TMZ/RT→TMZ). The total targeted number of subjects to be randomized is 750 (approximately 375 in each arm).

Experimental arm: Standard radiotherapy (60 Gy in 30 fractions over 6 weeks) + TMZ 75 mg/m² orally (PO) daily for 6 weeks (during RT) and MRZ dose 0.8 mg/m² intravenously (IV) at days 1, 8, 15, 29 and 36.

This is followed, after 4-week break, by up to 6 cycles of maintenance TMZ 150-200 mg/m² PO on days 1-5 of a 28-day cycle and up to 18 cycles of maintenance MRZ treatment (0.8 mg/m² IV) at days 1, 8, 15 of a 28-day cycle until disease progression, unacceptable toxicity or withdrawal of consent.

Continuation of maintenance TMZ beyond 6 cycles is not encouraged but will not constitute a protocol violation as long as it does not exceed 12 cycles in total.

Control arm: Standard RT (60 Gy in 30 fractions over 6 weeks) + TMZ 75 mg/m² PO daily for 6 weeks (during RT) then (after 4-week break) up to 6 cycles of maintenance TMZ 150-200 mg/m² PO on days 1-5 of a 28-day cycle.

Continuation of maintenance TMZ beyond 6 cycles is not encouraged but will not constitute a protocol violation as long as it does not exceed 12 cycles in total.

Subjects who at the start of the study are planning to get tumor-treating-fields (TTF) treatment are excluded from study entry, however those who decide after completing the concomitant part of the treatment to get TTF as part of their adjuvant treatment will not be discontinued, nor will they be considered protocol violators.

Study treatment was discontinued for a subject in the event of:

- Progressive disease
- Unacceptable overall toxicity for all drugs.
- Protocol violation
- Loss to follow-up
- Patient significant non-compliance
- Pregnancy
- Physician/Patient decision
- Death

An end-of-treatment visit had to be performed, and follow-up for survival, subsequent therapy and date of progressive disease (PD) were collected, whenever feasible.

Subjects had the right to withdraw from the study at any time for any reason.

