12.1.1. Treatment-emergent adverse events (TEAEs)

Adverse events will be analyzed in terms of TEAEs which are defined as AEs occurring or worsening on or after the date of start of treatment and within 30 days after the last treatment administration. AEs present at baseline which resolve during treatment and occurred again (at any grade) are considered TEAEs. AEs present at baseline which did not resolve within 30 days of the last treatment or which resolved but did not occur again are excluded from TEAEs.

Unless otherwise specified, summary of TEAEs will be provided for the whole study time and per period, overall and per treatment arm.

An overall summary of TEAEs will be provided for:

- subjects with at least one TEAE;
- subjects with at least one TEAE related to any study drug;
- subjects with at least one treatment-emergent serious AE (SAE)
- subjects with at least one treatment-emergent serious AE (SAE) related to any study drug;
- subjects with at least one CTCAE Grade 3 or 4 TEAE;
- subjects with at least one CTCAE Grade 3 or 4 TEAE related to any study drug;
- subjects with at least one TEAE leading to death (Grade 5);
- subjects with at least one TEAE leading to death (Grade 5) related to any study drug;
- subjects with at least one TEAE leading to dose reduction;
- subjects with at least one TEAE leading to dose interruption;
- subjects with at least one TEAE leading to study drug withdrawal;

In addition, TEAEs will be summarized per SOC and per PT for the following:

- all TEAEs;
- TEAEs, occurring for more than 10% of subjects in any treatment group;
- TEAEs related to any study drug (TMZ, MRZ);
- CTCAE Grade 3 or 4 TEAE;
- CTCAE Grade 3 or 4 TEAE related to any study drug;
- TEAEs by age group, for the whole study time only;
- TEAEs by sex, for the whole study time only;
- TEAEs by race, for the whole study time only;
- Treatment-emergent serious AEs (SAEs);
- Treatment-emergent serious AEs (SAEs) related to any study drug;
- TEAEs leading to death;
- TEAEs related to any study drug leading to death;
- TEAEs leading to dose reduction;
- TEAEs leading to dose interruption;
- TEAEs leading to study drug withdrawal.

Subjects with multiple occurrences of the same event will be counted only once per subject for each summary. Results will be reported in descending order of overall subject frequency in the overall column (unless otherwise specified) by SOC and by PT within the SOC. For summaries

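### SAP 12 compares adverse events as crude percentages over unequal planned treatment time, and its TMZ-dated periods leave some events of off-schedule patients in no period

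*SAP*

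**What the plan says.** **Summary measure.** SAP 5.2.4 and 12.1.1 define the safety output as counts and percentages of patients, each patient counted once per summary. An event qualifies if it starts or worsens between the start of treatment and 30 days after the last administration. Unless otherwise specified, a "summary of TEAEs will be provided for the whole study time and per period, overall and per treatment arm". SAP 12.1.3 applies the same layout to the events of special interest (AESIs). SAP 10 describes exposure by arm, but no adverse-event table uses it as a denominator.

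**Planned treatment.** Protocol 5.3: "In the standard arm, patients will receive up to 6 cycles of TMZ as maintenance". SAP 5.1 says that TMZ beyond 6 cycles "will not constitute a protocol violation as long as it does not exceed 12 cycles in total". The MRZ arm may receive "up to 18 cycles of maintenance MRZ treatment" (SAP 5.1).

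**Periods.** Under SAP 12 the concomitant period will "end 27 days after the day of the last administration of radiation therapy and before the start of adjuvant TMZ period whichever occurred first". Next, the adjuvant period opens at the first adjuvant TMZ dose. The MRZ-alone period "will start 28 days after the first day of administration of the last cycle of adjuvant TMZ". Protocol 8.2.3.2 dates these two periods from TMZ in the same way.

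**Courses the protocol allows.** Protocol 5.3 provides that if "one drug (TMZ or MRZ) is discontinued for reasons other than disease progression, the other will then continue as a single agent". Protocol 5.5.3 lets TMZ be skipped in a cycle while MRZ is given, and lets an adjuvant cycle start up to 14 days late for TMZ toxicity. Protocol 5.5 adds: "Treatment (MRZ +TMZ) may be administered -1 / +3 days of a scheduled dose for reasons other than toxicity".

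**The concern.** A patient watched for longer has more chance of a first event, whatever the drug does. If MRZ patients are treated for longer, part of any excess in their crude percentages is observation time, and the percentages alone cannot show how much.

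The by-period tables are the natural remedy, because they compare arms over similar stretches of treatment. They can do so only if every event has a period. Two of the four periods take their start date from adjuvant TMZ, and the protocol allows courses in which that date does not exist or comes late.

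At stake is how the risk side of benefit/risk is read in both the primary and the long-term reports, since SAP 3 includes all of section 12 in each.

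**Working it through.** **1. The plan's own figure.** 6 cycles of MRZ+TMZ plus 12 of MRZ alone = 18 cycles (Protocol 5.2, 5.3), as stated. Planned duration is 6 + 4 + 6×4 = 34 weeks in control, 6 + 4 + 12×4 = 58 weeks if control takes 12 TMZ cycles, and 6 + 4 + 18×4 = 82 weeks with MRZ.

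**2. Longest TEAE window.** The last TMZ dose is on day 5 and the last MRZ dose on day 15 of the final cycle, plus 30 days:
- control, 6 cycles: 10 + 5×4 + 5/7 + 30/7 = 35.0 weeks
- control, 12 cycles: 10 + 11×4 + 5/7 + 30/7 = 59.0 weeks
- MRZ, 18 cycles: 10 + 17×4 + 15/7 + 30/7 = 84.4 weeks

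**3. Equal hazard, full follow-up.** Assumptions: the same constant event hazard h in both arms; the same exponential PFS; treatment to progression or planned end. Time at risk is T = min(PFS + 30 days, window). Incidence is the mean of 1 − exp(−hT), with h set so that control reads 20%.

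| Median PFS (months, assumed) | Control | MRZ, full follow-up | MRZ, 28 April 2020 cut-off |
|---|---|---|---|
| 5 | 20% | 25.4% | 22.1-22.4% |
| 7 | 20% | 28.0% | 23.0-23.5% |
| 9 | 20% | 29.9% | 23.6-24.3% |
| 12 | 20% | 32.0% | 24.2-25.1% |

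Hand check at 7 months: mean time at risk is 26.4 v 41.1 weeks, and 1 − 0.80^(41.1/26.4) = 29%. This is slightly above 28.0% because time at risk varies between patients.

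**4. The cut-off (last column).** SAP 2 gives 616 patients randomised at 28 April 2020. Protocol 1.1 gives 286 at 10 July 2019, in a paragraph read here as referring to this trial. So 616 − 286 = 330 patients (54%) had at most 293 days (42 weeks) of observation, and none of them could approach 84 weeks. The column assumes uniform accrual within each stretch and the first 286 enrolled over 9-15 months, with h reset so that control reads 20%.

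**5. Longer TMZ in control.** If every control patient took 12 TMZ cycles, the full-follow-up hazard from step 3 would give 24-27% in control against 25-32% with MRZ.

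**6. Period coverage, day by day.** Assumed calendar: radiotherapy on days 1-40 and the first adjuvant dose due on day 40 + 28 = 68. The TEAE windows are then 242 and 588 days, 3 days shorter than in step 2. For an MRZ patient with no adjuvant TMZ, the concomitant period ends on day 40 + 27 = 67 and nothing opens on day 68.

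| Course | TEAE days in no period |
|---|---|
| Exactly on schedule, either arm | 0 |
| No adjuvant TMZ, 1 MRZ cycle | 28 |
| No adjuvant TMZ, 6 MRZ cycles | 6×28 = 168 |
| No adjuvant TMZ, 18 MRZ cycles | 18×28 = 504 of 588 |
| Cycle 1: TMZ skipped, MRZ given | 28 |
| The same after a 14-day delay | 28 + 14 = 42 |
| Adjuvant start 14 days late, either arm | 14 |
| Adjuvant start within the +3-day dosing window, either arm | up to 3 |

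These counts let the last MRZ cycle open the follow-up period. If follow-up is also read as undefined without TMZ, the three no-adjuvant-TMZ rows become 45, 185 and 521.

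**The case against.** The percentage of patients with an event under each assigned strategy is a legitimate description, and SAP 10 tabulates treatment duration, cycles and dose intensity by arm, so a reader can see that exposure differs. That stands. It does not tell the reader what the contrast would be at equal time at risk.

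A reader might infer that the MRZ percentages in the primary report are inflated by 5-12 points. The documents do not support this. The primary report keeps the April 2020 cut-off, which brings the illustration down to about 2-5 points even before early stopping, and SAP 3 itself expects MRZ exposure below plan after the IDMC advice. The full-follow-up figures bear on the long-term analysis, which is descriptive.

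A reader might also infer that MRZ-alone events in general drop out. They do not. A patient who stops TMZ after at least one adjuvant cycle is caught by the MRZ-alone period, and events without a period still appear in the whole-study tables and listings: they are misplaced, not lost. The SAP's gloss on that period, MRZ given by itself once TMZ has stopped, shows that these patients were meant to be covered, but their start date cannot be computed. The single-agent sentence in Protocol 5.3 follows a description of maintenance, so extending it to TMZ stopped during radiotherapy is an inference.

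The late-start gap is small, affects both arms, and in a whole-cycle delay falls on days when no study drug is given. Nor do the two issues cancel: they sit in different tables. Neither bears on the IDMC's neurotoxicity observation, which predates SAP v2.0.

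**Conclusion.** The point holds in two separate and limited parts.

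First, the arms are compared on crude percentages with no rate per time at risk, although planned adjuvant treatment differs by up to a factor of three in cycles. Under an equal constant hazard, a 20% control incidence would read about 25-32% with MRZ under full follow-up and about 22-25% at the primary cut-off. These figures rest on assumed PFS medians, a constant hazard and an assumed accrual pattern. Extended TMZ in control and early MRZ stopping shrink the gap and together could reverse it, so realised exposure decides both size and sign.

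Second, the period definitions are incomplete for three courses: no adjuvant TMZ cycle, a first cycle with TMZ skipped but MRZ given, and a late adjuvant start in either arm. Patients on schedule lose nothing. The number affected is not documented. If 1-10% of about 375 MRZ patients took adjuvant MRZ without adjuvant TMZ (an assumption), that would be about 4-38 patients.

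Both are worth correcting before the tables are programmed. Neither shows that the planned safety conclusions would be wrong.

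**What to change.** **(a)** Beside the percentages, report patients with a first event per 100 patient-months at risk, by arm, for all TEAEs, Grade 3-4 TEAEs, SAEs and each AESI category. These rates assume a roughly constant hazard, so they should accompany the percentages and not replace them.

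**(b)** Make the periods contiguous and mutually exclusive:
- Concomitant: from the first study treatment to the day before the first adjuvant dose of either drug, or to the end of the TEAE window if there is none.
- Adjuvant TMZ: opens at that first adjuvant dose if the patient receives any adjuvant TMZ, and keeps its present end, 27 days after day 1 of the last adjuvant TMZ cycle.
- MRZ-alone: opens the day after that end if MRZ continues, or at the first adjuvant MRZ dose if there is no adjuvant TMZ cycle. It keeps its present end, 27 days after day 1 of the last MRZ cycle.
- Follow-up: opens 28 days after day 1 of the last cycle of either drug and runs to 30 days after the last administration.

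MRZ-alone should not open at the first MRZ dose after TMZ stops. That is day 8 of the last combined cycle, so days 8-28 would leave the adjuvant period in the MRZ arm but stay in it for control.

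With these definitions, every TEAE day in the courses tabulated above falls in exactly one period. The cost is SAP wording, a note that Protocol 8.2.3.2 is refined, and programming on data already collected. No clinical rule changes.

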### **8.2.3.2 Safety analysis**

All analyses will be performed in the safety population:

The safety and tolerability will be followed from study treatment initiation through up to 30 days after the last administration of study treatment.

The safety analyses will be reported for the whole study time and by treatment period as defined below:

The chemoradiation period (TMZ/RT or TMZ/RT+MRZ) will start on the day of the first administration of radiation therapy and end 27 days after the day of the last administration of radiation therapy.

The adjuvant TMZ period (adjuvant TMZ +/- MRZ) will start on the day of the first dose of adjuvant TMZ and end-up 27 days after the first day of administration of the last cycle of adjuvant TMZ.

The maintenance marizomib period (MRZ) will start 28 days after the first day of administration of the last cycle of adjuvant TMZ and end-up 27 days after the first day of administration of the last cycle of maintenance marizomib.

The follow-up period (FUP) will start 28 days after the first day of administration of the last cycle of maintenance marizomib up to 30 days after the last administration of marizomib

Baseline value will be defined as the last value on or before the first dose of study treatment is administered; if multiple values are present for the same date, the average of these values will be used as the baseline. For patients who were not treated, the value on or prior to randomization date will be used. Baseline laboratory and AE grades will be presented together with other baseline data in the ITT population.

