10.1. Treatment Duration

Radiotherapy

Radiotherapy consists of a conventionally fractionated regimen delivering a total dose of 60 Gy in 30 fractions in 6 weeks, a fraction of 2 Gy once daily, 5 days per week. The RT duration (in weeks) is defined as $(\text{last RT dose date} - \text{first RT dose date} + 1) / 7$.

Chemotherapy

The treatment start date is the date of the first dose of study drugs (MRZ or TMZ). The treatment end date is the date on which the decision was made by investigator to discontinue subject's treatment. Whenever the treatment is given in cycles and the last planned day of treatment is not the last day of the cycle, the total duration of the treatment must account for this by adding the appropriate number of days to complete the last cycle.

Temozolomide is given on a daily basis for 6 weeks during RT (concomitant phase) and after a 4-week interval, TMZ is given on days 1-5 of a 28-day cycle (maintenance phase).

- The concomitant TMZ duration (in weeks) is defined as $(\text{last concomitant TMZ dose date} - \text{first concomitant TMZ dose date} + 1) / 7$.
- The maintenance TMZ duration (in weeks) is defined as $([\text{maintenance TMZ end date} - \text{maintenance TMZ start date}] + 1 + (28 - n)) / 7$ where n is the last day of administration of the last cycle, ie, Day 1, 2, 3, 4, or 5.

Marizomib is given on Days 1, 8, 15, 29, 36 for one cycle of 6 weeks during radiotherapy (concomitant phase) and after a 4-week interval, MRZ is given on days 1,8,15 of a 28-day cycle (maintenance phase).

- The concomitant MRZ duration (in weeks) is defined as $([\text{last concomitant MRZ end date} - \text{first concomitant MRZ start date}] + 1 + (42 - n)) / 7$.
- The maintenance MRZ duration (in weeks) is defined as $([\text{maintenance MRZ end date} - \text{maintenance MRZ start date}] + 1 + (28 - n)) / 7$, where n is the last day of administration of the last cycle, ie, Day 1, 8, or 15.

For subjects who are still on treatment at the time of study closure or clinical cutoff, the planned cycle length will be used to calculate the end date and for both drugs the treatment duration (in weeks) is defined as: $[\text{the study treatment end date} - \text{the first study drug start date} + 1] / 7$.

Descriptive statistics will be provided for treatment duration and total number of cycles by treatment arm.

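### The SAP's follow-up safety period varies with the day of the last dose (7 days after a fully dosed last temozolomide cycle, 17 after a marizomib one), but its adverse event tables show crude percentages by arm

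*SAP*

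**What the plan says.** The opening text of SAP section 12 divides safety follow-up into periods. The adjuvant TMZ period is to "end up to 27 days after the first day of administration of the last cycle of adjuvant TMZ", and the maintenance MRZ period closes by the same rule on its own last cycle. The follow-up period, described as the time after every treatment has stopped, "will start 28 days after the first day of administration of the last cycle of maintenance MRZ or adjuvant TMZ up to 30 days", these 30 days being counted from the last dose of MRZ or TMZ.

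The dosing days are in SAP 10.1: "TMZ is given on days 1-5 of a 28-day cycle (maintenance phase") and "MRZ is given on days 1,8,15 of a 28-day cycle (maintenance phase").

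SAP 12.1.1 sets the reporting: "Unless otherwise specified, summary of TEAEs will be provided for the whole study time and per period, overall and per treatment arm". SAP 12.1.3 does the same for the adverse events of special interest (AESIs). Each subject counts once per summary (SAP 12.1.1), and the safety endpoint is frequencies and percentages (SAP 5.2.4). No person-time rate or time-to-event method for adverse events appears in SAP section 12 or in Protocol 8.2.3.2. The safety objective in SAP 4.2 is comparative, and SAP section 3 puts all of section 12 into both the primary and the long-term reports.

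Protocol 8.2.3.2 defines the same period by marizomib only: "The follow-up period (FUP) will start 28 days after the first day of administration of the last cycle of maintenance marizomib".

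**The concern.** The two ends of the window are tied to different events: the start to the first day of the last cycle, the end to the last dose. The two drugs finish dosing on different days of the same 28-day cycle, so the window length depends on which drug was given last, and that depends largely on the arm.

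Readers will use this period to judge whether toxicity persists after stopping. The AESIs are ataxia, dysarthria and hallucination/delirium, and the IDMC singled out severe neurological and neuropsychiatric disorders. If one arm is observed for longer in this period, a percentage of patients with at least one event mixes persistence of toxicity with length of observation.

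**Working it through.** The plan states no length for this period, so there is no figure to reproduce. The length follows from its rules.

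**Inputs.** Call the first day of the last cycle Day 1.
- The preceding period ends 27 days after Day 1: 1 + 27 = Day 28 (SAP 12).
- Follow-up starts 28 days after Day 1: 1 + 28 = Day 29 (SAP 12). The two boundaries meet, which supports inclusive counting.
- Follow-up ends 30 days after the last dose: last-dose day + 30 (SAP 12).
- Last planned dose in a cycle: Day 5 for TMZ, Day 15 for MRZ (SAP 10.1).

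**Length.** (last-dose day + 30) − 29 + 1 = last-dose day + 2.

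| Last dose | Window | Length |
|---|---|---|
| TMZ Day 5 (full) | Days 29–35 | 7 days |
| TMZ Day 1, 2, 3 or 4 | Day 29 to Day 31, 32, 33 or 34 | 3, 4, 5 or 6 days |
| MRZ Day 15 (full) | Days 29–45 | 17 days |
| MRZ Day 8 | Days 29–38 | 10 days |
| MRZ Day 1 | Days 29–31 | 3 days |

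For full-cycle patients the ratio is 17/7 = 2.4. Ten of the 17 days (59%) lie beyond the full-cycle control window. Counted as elapsed time, the lengths are 6 and 16 days. The same 17 days apply to a patient who stops during combined TMZ + MRZ cycles with MRZ on Day 15 as the last dose. A marizomib-arm patient who has stopped MRZ and ends on TMZ alone has the TMZ window of 7 days. The −1/+3 day tolerance in Protocol 5.5 moves the end by the same number of days and is ignored here.

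**Average gap.** An incomplete last cycle removes up to 14 days from a marizomib window (17 to 3), and ending on TMZ alone removes 10. It removes at most 4 from a control window (7 to 3). The average gap should therefore be below 10 days. The documents do not give the distribution of last-dose days, so it cannot be computed.

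**Effect on a crude percentage.** Assume a constant event rate, equal in both arms, full-cycle patients, and a denominator of patients entering the period. Then P(at least one event) = 1 − exp(−rate × days/30). The rates are assumptions; no document gives them.

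| Assumed events per 30 days | 7 days | 17 days |
|---|---|---|
| 0.1 | 2.3% | 5.5% |
| 0.2 | 4.6% | 10.7% |
| 0.4 | 8.9% | 20.3% |

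For 0.2: 1 − exp(−0.2 × 7/30) = 1 − exp(−0.0467) = 4.6%, and 1 − exp(−0.2 × 17/30) = 1 − exp(−0.1133) = 10.7%. With no true difference, the apparent risk ratio is about 2.3 to 2.4.

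**The case against.** The case for leaving this alone has several parts, and much of it stands.

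- A reader might take 7 and 17 days as fixed for every patient in each arm. They are not. SAP 10.1 expects last MRZ doses on Day 1, 8 or 15; Protocol 5.5.1 lets doses be skipped; and Protocol 5.3 lets one drug continue after the other stops. Some marizomib patients will have a shorter window than a full-cycle control patient.
- A reader might infer a biased formal comparison of the arms. No between-arm test of adverse events is planned, and the tables are descriptive. The maintenance MRZ period already has no control counterpart, so not every period table invites comparison.
- A reader might infer that the trial's main safety results are distorted. They are not. Whole-study TEAE summaries use one rule in both arms, 30 days after the last administration, and the table of deaths within 30 days is already anchored on the last dose. No event is gained or lost; only its period label changes.
- The percentages above are illustrations. After discontinuation, Protocol 7.2.1 asks mainly for follow-up of suspected reactions that began on treatment and for new SAEs, although Protocol 6.3.1 also lists adverse events at the end-of-treatment visit. An all-event rate may not apply, and the SAP states no denominator for period tables.
- Protocol 8.2.3.2 could be read as leaving control patients with no follow-up period. The SAP has already added TMZ to the definition, so this is a gap in the protocol wording and not a missing analysis.
- Ending the treatment period at the last drug dose could put a patient who is still receiving RT into follow-up, and could conflict with SAP 10.1, which counts the rest of the last cycle as treatment duration. Both points are valid and shape the fix.

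None of this removes the mismatch of anchors. On the planned dosing days a control window cannot exceed 7 days, while a marizomib window can reach 17.

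**Conclusion.** The point holds in a limited form. The rule in SAP section 12 makes the length of the follow-up period depend on the last drug given, and the plan reports that period by arm as crude percentages with no allowance for time observed. At equal event rates the marizomib arm would tend to show more patients with events after stopping.

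The day counts are exact for patients who complete the last cycle's dosing days on schedule. The percentages also rest on an assumed constant and equal rate. The defect is confined to the follow-up-period TEAE and AESI tables. The documents do not support saying that the overall safety comparison is biased, or that any excess seen in that table must be an artefact. The correction should still be made, because it needs no new data and this table bears directly on persistence of toxicity.

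**What to change.** In SAP section 12 and Protocol 8.2.3.2, define the follow-up period in both arms as days 1 to 30 after the last administration of any study treatment, taking the latest of RT, TMZ or MRZ. End the preceding safety period on that day, for safety tabulation only, and leave the exposure durations in SAP 10.1 unchanged. Including RT keeps patients who are still being irradiated out of follow-up. Say in SAP 12.1.1 whether the last treatment administration includes RT, so that the TEAE window matches, and state the denominator for the period tables. The definition also gives a start date for patients who stop before any adjuvant cycle, who have none under the present rule.

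The cost is SAP and protocol wording plus one derivation. The downside is that events in the rest days of the last cycle move from the treatment period to follow-up in both arms. The last cycle then contributes 5 days (TMZ) or 15 days (MRZ) to the treatment period. Over six full cycles that is 5 × 28 + 5 = 145 against 5 × 28 + 15 = 155 days, a 7% difference, compared with 7 against 17 days (143%) in follow-up now.

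Alternatively, keep the boundaries and report exposure-adjusted incidence for the follow-up period by arm. This moves no events between periods.
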